12.2.5 Compensation to Subjects/Patients and Investigators

Lipum AB is providing insurance in order to indemnify (legal and financial coverage) the Investigator/center against claims arising from the study, except for claims that arise from malpractice and/or negligence.

The compensation of the subject/patient in the event of study-related injuries will comply with the applicable regulations.

13 STRUCTURED RISK ANALYSIS

13.1 Potential Issues of Concern

13.1.1 Level of Knowledge About Mechanism of Action

[REDACTED]

13.1.2 Previous Exposure of Human Beings with the Test Product(s) and/or Products with a Similar Biological Mechanism

First-in-human study, first-in-class drug, not applicable.

13.1.3 Can the Primary or Secondary Mechanism be Induced in Animals and/or in Ex-vivo Human Cell Material?

[REDACTED]

13.1.4 Selectivity of the Mechanism to Target Tissue in Animals and/or Human Beings

13.1.5 Analysis of Potential Effect

13.1.6 Pharmacokinetic Considerations

13.1.7 Study Population

Up to 48 healthy male and female volunteers, and 1 cohort of 8 RA patients will be enrolled, aged between 18-65 years. Females of childbearing potential may be enrolled if they agree to use appropriate contraception.

[figure not shown]
13.1.8 Interaction with Other Products

Metabolism and potential metabolic interactions have not been investigated. Based on the fact that both SOL-116 and its target BSSL being proteins, and since SOL-116 is not directly binding proinflammatory cytokines, there are no expected drug-drug interactions with small molecule drugs.

In the RA cohort, all patients will receive concomitant treatment with methotrexate (MTX). No pharmacodynamic interactions are expected as MTX affect the folic acid synthesis and SOL-116 affects cells in the immune system.

13.1.9 Predictability of Effect

The PK behavior of SOL-116 in the preclinical studies appears predictable and in line with what is expected after s.c. injections of a monoclonal antibody.

13.1.10 Can Effects be Managed?

No antidote is available. Treatment of adverse effect will be symptomatic, tailored to the nature of the events. Subjects with a history or known hypersensitivity or allergy are excluded from participation in the study. There is also immediate access to equipment, qualified staff and an intensive care unit in case of an acute emergency.

13.2 Synthesis

This is a First-in-Human trial with a First-in-Class novel investigational medicinal product. Given the available nonclinical safety data, the selected starting dose and the oversight of dose escalation steps by a Safety Review Committee and ethics committee, the overall risk assessments are acceptable in these populations of healthy volunteers and RA patients, given the dose and the close supervision during the study.

13.3 Category study

Conclusions	 Based on the risk analysis the study can be performed without additional conditions.
	 Based on the risk analysis the study can be performed with the following additional conditions:
	 Based on the risk analysis the study cannot be performed. The main issue is:

2 LIST OF ABBREVIATIONS AND DEFINITIONS OF TERMS

ADA	Anti-drug antibodies
ADaM	Analysis data model
AE	Adverse event
ALT	Alanine aminotransferase
AST	Aspartate aminotransferase
ATC	Anatomic Therapeutic Chemical
BMI	Body mass index
BSSL	Bile salt-stimulated lipase
CCP	Cyclic citrullinated peptide
COVID-19	Coronavirus disease 2019
CRP	C-reactive protein
CS	Clinical significance
DAS28	Disease activity score 28
DBL	Database Lock
ECG	Electrocardiogram
eCRF	Electronic case report form
eGFR	Estimated glomerular filtration rate
EOS	End-of-study
ESR	Erythrocyte sedimentation rate
FIH	First-in-human
FSH	Follicle-stimulating hormone
FU	Follow-up
GGT	Gamma-glutamyltransferase
GIT	Gastro-intestinal tract
HDL	High-density lipoprotein
hsCRP	High sensitive C-reactive protein
ICH	International Council for Harmonisation (of Technical Requirements for Pharmaceuticals for Human Use)
IEC	Independent ethics committee
IFN _γ	Interferon gamma
LDH	Lactate dehydrogenase

LDL	Low-density lipoprotein
LLOQ	Lower limit of quantification
MedDRA	Medical Dictionary for Regulatory Activities
MH	Medical history
MCP	Monocyte chemoattractant protein
MTX	Methotrexate
N	Number of subjects/patients
NCS	Non-clinical significance
PCV	Packed cell volume
PD	Pharmacodynamic(s)
PK	Pharmacokinetic(s)
PKAP	Pharmacokinetic analysis plan
PR	PR interval of the ECG
PT	Preferred Term
QRS	QRS interval of the ECG
QTcF	Corrected QT interval using Fridericia's formula
RA	Rheumatoid arthritis
RBC	Red blood cell
RDW-CV	Red blood cell distribution width
RR	RR interval of the ECG
SAE	Serious adverse event
SAP	Statistical analysis plan
SAS	Statistics analysis system
SARS-CoV-2	Severe acute respiratory syndrome-coronavirus-2
SC	Subcutaneous(ly)
SD	Standard deviation
SDTM	Study data tabulation model
SI	International system
SOC	System organ class
SOE	Schedule of events
SRC	Safety review committee
TEAE	Treatment-emergent adverse event

TESAE	Treatment-emergent serious adverse event
TNF _α	Tumor necrosis factor alpha
ULOQ	Upper limit of quantification
VAS	Visual analogue scale
VS	Vital signs
WBC	White blood cell
WHO	World Health Organization

3 INTRODUCTION

3.1 Preface

This statistical analysis plan (SAP) is based on protocol LPM-116-001 Amendment 6, dated 05 August 2024. The SAP provides details of data handling procedures and statistical analysis methods for safety, tolerability and pharmacodynamic variables. It also outlines the statistical programming specifications for tables and listings, and other analyses details not provided in the study protocol.

The pharmacokinetic analysis plan (PKAP) is not part of this SAP. It will be described in a separate document.

The unblinding process and Database Lock (DBL) will be performed after each part are completed.

4 DOCUMENTS USED

Clinical Study Protocol (CSP)

A Randomized, Double-Blind, Placebo-Controlled, First-in-Human Phase I Study Evaluating Safety, Tolerability and Pharmacokinetics of Single Ascending Doses of SOL-116 (a Humanized Monoclonal Anti-BSSL Antibody) in Healthy Subjects and Patients with Rheumatoid Arthritis, LPM-116-001, Amendment 6, and Date of Release: 05-Aug-2024, C1 – COVID-19 CSP Addendum, Version 9, Date of Release: 08-Apr-2022.

Source/CRF

- Part 1
 - eCRF OpenClinica, Date of Release: 18-Sep-2023
 - eCRF ClinSpark, Date of Release: 12-Dec-2022
- Part 2
 - eCRF OpenClinica, Date of Release: 12-Feb-2024
- Part 3
 - eCRF OpenClinica, Date of Release: 05-Apr-2024
 - eCRF ClinSpark, Date of Release: 20-Sep-2022

4.1 Study Objectives

For single dosing (Parts 1 and 2):

Primary objective:

- To evaluate the safety and tolerability of single ascending doses of SOL-116 in healthy subjects and rheumatoid arthritis (RA) patients.

Secondary objective:

- To determine single dose pharmacokinetic (PK) characteristics of SOL-116 in healthy subjects and RA patients.
- To assess the immunogenicity of SOL-116 after single SC doses in healthy subjects and RA patients.

Exploratory objective:

- To evaluate the effect of single ascending doses of SOL-116 on bile salt-stimulated lipase (BSSL) concentration in the blood of healthy subjects and RA patients.
- To evaluate the pharmacodynamic (PD) effect of single ascending doses of SOL-116 on inflammatory biomarkers in the blood of healthy subjects and RA patients.

For multiple dosing (Part 3):

Primary objective:

- To evaluate the safety and tolerability of multiple dosing of SOL-116 in healthy subjects.

Secondary objective:

- To determine multiple dose PK characteristics of SOL-116 in healthy subjects.
- To assess the immunogenicity of SOL-116 after multiple SC doses in healthy subjects.

Exploratory objective:

- To evaluate the effect of multiple doses of SOL-116 on BSSL concentration in the blood of healthy subjects.
- To evaluate the PD effect of multiple doses of SOL-116 on inflammatory biomarkers in the blood of healthy subjects.

4.2 Data Sources

All analyses will be carried out using data from the eCRF (OpenClinica, ClinSpark) and external data including external laboratory data and the protocol deviation list (if applicable). Datasets will be extracted from OpenClinica, ClinSpark and converted to Study Data Tabulation Model (SDTM) datasets and Analysis Data Model (ADaM) datasets.

5 OVERALL STUDY DESIGN AND PLAN

5.1 Study Design

This is a randomized, double-blind, placebo-controlled Phase I, first-in-human (FIH) study in three parts: healthy subjects and adult RA patients (Parts 1 and 2) and multiple SC doses in healthy subjects (Part 3).

The study will be monitored by a safety review committee (SRC). The intent of the SRC is to ensure that treatment does not pose undue risk to subjects/patients. Safety, tolerability and available PK data will be assessed by the SRC after each cohort before ascending to the next dose level.

Part 1

Eligibility will be assessed during a screening period of up to 28 days. For the treatment period, subjects/patients will check into the clinic one day prior to dosing (Day -1). On Day 1, all subjects/patients will receive SOL-116 in a fasted state (after an overnight fast of at least 10 hours). Subjects/patients will be released from the clinic on Day 2 (Part 1), after all required study

procedures are completed and if medically justified. If medically indicated and/or based on emerging data, patients may be asked to return on Day 3 for additional safety assessments (optional visit). Furthermore, in both parts the clinic stay may be extended up to Day 7 if medically indicated and/or based on emerging data. In total, patients will return to the clinic for up to 8 ambulant visits up to Day 63. Subjects/patients will return to the clinic on Day 90 for an end-of-study (EOS)/ follow-up visit.

Part 2

Eligibility will be assessed during a screening period of up to 42 days. For the treatment period, patients will check into the clinic one day prior to dosing (Day -1). On Day 1, all patients will receive SOL-116 in a fasted state (after an overnight fast of at least 10 hours). Patients will be released from the clinic on Day 2, after all required study procedures are completed and if medically justified. If medically indicated and/or based on emerging data, patients may be asked to return on Day 3 for additional safety assessments (optional visit). Furthermore, the clinic stay may be extended up to Day 7, if medically indicated and/or based on emerging data. In total, patients will return to the clinic for up to 8 ambulant visits up to Day 63. Patients will return to the clinic on Day 90 for an EOS/follow-up visit.

Part 3

Eligibility will be assessed during a screening period of up to 28 days. For the first dose, subjects will check into the clinic one day prior to dosing (Day -1). On Day 1, all subjects will receive SOL-116 or placebo. Subjects will be released from the clinic on Day 2, after all required study procedures are completed and if medically justified. If medically indicated and/or based on emerging data, the clinic stay may be extended up to Day 7. Subjects will return to the clinic for 15 ambulant visits up to Day 154. Subjects will return to the clinic on Day 169 for an EOS/follow-up visit. After the second and third dose, a phone contact will be made (3 to 7 days after the dose) with the subject to ensure no new adverse events or if new medication has been added.

Based on SRC recommendations, the visit schedule may be adjusted.

5.2 Study Drug Administration

The SOL-116 will be administered as abdominal subcutaneous(ly) (SC) injection(s). The injection volume will be no more than 2.0 mL per injection. The number of SC injections given to administer the single dose in Cohort 2 to Cohort 7 may be increased to up to 4 injections. For more information see the CSP.

Subjects/patients will not be allowed to eat or drink (except water) from 10 hours prior to the administration of study drug or placebo.

All study drugs will be dispensed by the Investigator or a person supervised by the Investigator. The time of administration of SOL-116 or placebo will be recorded in the eCRF.

In Part 3, the same applies but 4 dose administrations (with maximum 4 injections per occasion) will be administered with 28 days' interval (in MD1).

In Part 2, there should be at least 24 hours between administration of SOL-116 and the preceding MTX dose and at least 24 hours between administration of SOL-116 and the subsequent MTX dose.

5.3 Study Details

The subject population will include healthy adult subjects (Cohort 1-6) and patients (Cohort 7) who satisfy all entry criteria.

Part 1

Up to 5 single doses are planned to be tested in 5 cohorts of 8 healthy subjects (6 active, 2 placebo) (Cohort 1 to Cohort 5). One additional cohort (Cohort 6) of 8 healthy subjects (6 active, 2 placebo) may be added based on emerging data, i.e. in total 40 or 48 subjects will be randomized and dosed.

Sentinel dosing will be employed in all cohorts. Thus, within each cohort initially 1 subject will receive SOL-116 and 1 subject will receive placebo. The remaining 6 subjects of the cohort may be dosed at least 48 hours after dosing of the initial 2 subjects of the cohort, provided no clinically significant safety issues, as judged by the Investigator, are noted in the 48 hours after dosing of the initial 2 subjects of the cohort.

After each cohort completes dosing, a dose escalation SRC meeting will take place. Escalation to the next higher dose level may occur only after evaluation of the safety/tolerability and available PK data up to and including 14 days post-dose of at least 6 evaluable subjects (subject assessed as pharmacokinetically evaluable at Day 14) and after approval by the independent ethics committee (IEC). This time point may be adjusted based on the PK data of previous cohorts if the SRC recommends.

Part 2

In a cohort of up to 8 RA patients (6 active, 2 placebo) will be randomized and dosed (Cohort 7), one of the single doses tested in healthy subjects will be tested.

The cohort with RA patients (Cohort 7) will be run after the completion of all cohorts with healthy subjects. The dose level of Cohort 7 will be determined based on the safety and PK results of all preceding cohorts and will not exceed that of the already given dose levels in healthy subjects. There should be at least 24 hours between administration of SOL-116 and the preceding methotrexate (MTX) dose and at least 24 hours between administration of SOL-116 and the subsequent MTX dose.

Sentinel dosing will be employed. Thus, initially 1 patient will receive SOL-116 and 1 patient will receive placebo. The remaining 6 subjects of the cohort can be dosed at least 48 hours after dosing, provided no clinically significant safety issues, as judged by the Investigator, are noted in the 48 hours after dosing of the initial 2 patients of the cohort.

Part 3

Up to two multiple dosing cohorts of 8 healthy subjects (6 active, 2 placebo) (Cohorts MD1 and MD2) are planned, i.e. in total up to 16 subjects will be randomized and dosed.

Sentinel dosing will be employed in all cohorts. Thus, within each cohort initially 1 subject will receive SOL-116 and 1 subject will receive placebo. The remaining 6 subjects of the cohort may be dosed at least 48 hours after dosing of the initial 2 subjects of the cohort, provided no clinically significant safety issues, as judged by the Investigator, are noted in the 48 hours after dosing of the initial 2 subjects of the cohort.

After each cohort completes dosing, a dose escalation SRC meeting will take place. Escalation to the next MD dose cohort may occur only after evaluation of the safety/tolerability and available PK data up to and including 28 days post last dose of at least 6 evaluable subjects (subject assessed as pharmacokinetically evaluable at Day 28) and after approval by the IEC. This time point may be adjusted based on the PK data of previous cohorts if the SRC recommends.

5.4 Sample Size

As this is a first in human study, no formal sample size calculation has been performed. The proposed sample size is considered sufficient to provide adequate information for the study objectives.

5.5 Study Flow Chart/Schedule of Events (SOE)

The study will consist of two parts.

In Part 1, there are a Screening period (Day -28 to Day -2), a treatment period (Day -1 to Day 63 ± 3), and a follow-up evaluation (Day 90 ± 3 days).

In Part 2, there are a Screening period (Day -28 to Day -2), a treatment period (Day -1 to Day 63 ± 3), and a follow-up evaluation (Day 90 ± 3 days).

In Part 3, there are a Screening period (Day -28 to Day -2), a treatment period (Day -1 to Day 154 ± 3), and a follow-up evaluation (Day 169 ± 5 days).

The complete schedules of prescheduled visits and all procedures for Part 1, Part 2, and Part 3 are presented in Table 5-1, Table 5-2, and Table 5-3 respectively in the CSP.

6 DESCRIPTION OF INCLUDED SUBJECTS

6.1 Analysis Populations

6.1.1 All-treated set

This analysis set includes all randomized subjects/patients who received study drug (at least one dose).

6.1.2 Safety set

This analysis set includes subjects/patients from the All-treated set who had at least one safety assessment post-baseline. The safety set will be employed in the analysis of tolerability and safety variables.

6.1.3 Immunogenicity set

This analysis set includes all subjects/patients who received the study treatment and had at least 1 post-dose immunogenicity sample collected.

6.1.4 Per-protocol set

This analysis set comprises all subjects/patients included in the All-treated set who did not violate the protocol in a way that might affect the evaluation of the effect of the study drug(s) on the primary endpoint, i.e., without major protocol violations or deviations. The Per-protocol set will be employed in the analysis of PK and exploratory variables.

6.1.5 PD (exploratory) set

This analysis set comprises all subjects/patients included in the All-treated set who did not violate the protocol in a way that might significantly affect the ability to analyze exploratory endpoints (i.e. RA patients who received more than 2 intra-articular injections in large joints and/or 6 intra-articular injections in small joints during the study are excluded).

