13. On Day 1 prior to dosing, and at 1, 4, 8, 24 (Day 2), 48 (Day 3, optional) and 72 hours (Day 4) post-dose.
14. On Day 1 prior to dosing. Based on emerging data, collection time points may be updated.
15. Only collected and analysed when the patient has given consent for the collection and future analysis of this sample in the informed consent form.
16. Fasting glucose and lipid status determined at Screening, pre-dose on Day 1, Day 14 and Day 35. α -tocopherol status determined pre-dose on Day 1, Day 14 and Day 35 only. S-calprotectin and hsCRP determined prior to dosing and 4 hours post-dose on Day 1, on Day 2, on Day 4, on Day 21, on Day 49 and on Day 90. Subjects should be fasting for at least 4 hours prior to blood sampling at Screening, and 10 hours prior to blood sampling on Day 1, Day 14 and Day 35. Rheumatoid factor and anti-CCP antibodies only at Screening. Urinalysis only at Screening, on Day -1, on Day 2, on Day 8, on Day 14, on Day 21, and on Day 90. At Screening, laboratory assessments may be repeated once, at the discretion of the Investigator.
17. If medically indicated and/or based on emerging data, the clinic stay may be extended up to Day 7.
18. Starting from study drug administration.
19. Prior to dosing and 4 hours post-dose.
20. 4 hours post-dose.
21. Up until study drug administration.
22. Spare patients not immediately included in the study may be kept in the clinic until it is decided whether these patients are to be included. If subjects are included > 48 hours after admission in the clinic on Day -1, the Day -1 assessments have to be repeated.

Table 5-3: Visit and Assessment Schedule for Repeated Dosing Part (every Q4W dosing) – Part 3

Study Period	Screening	Treatment period													FU/EOS
		Visit 1 ¹	Visit 2 ²		Visit 3	Visit 4 ³	Visits 5-6	Visit 7 (dosing day) ⁴	Visit 8 (dosing day) ⁴	Visit 9 (dosing day)	Visits 10-11	Visits 12-17			
Assessments / Study days (visit windows in days)	Day -28 to Day -2	Day -1	Day 1	Day 2	Day 4 (72 hrs) (±1)	Day 8 (±1)	Days 11 and 15 (±1)	Day 29 (±1)	Day 57 (±3)	Day 85 (±3)	Day 86 and 88	Days 92, 95, 99, 113, 140, 154 (±3)	Day 169 (±5)		
Informed consent	X														
Eligibility criteria	X	X													
Randomization			X												
Demographics	X														
Height	X														
Weight	X	X								X	X	X			
BMI	X														
QuantiFERON® test ⁵	X														
Vital signs (blood pressure, pulse rate, temperature)	X		X ¹⁴	X	X	X		X ¹⁴	X ¹⁴	X ¹⁴	X	X ¹⁵	X		

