12. Having evidence of active TB or latent TB at Screening as assessed by chest X-ray (RA patients only) and/or by QuantiFERON®-test. Applicable for RA patients only: in case of rescreening within three months after Screening, negative results from the initial chest X-ray and/or QuantiFERON®-test performed during Screening do not need to be repeated.
13. Subjects/patients who are currently enrolled in or have recently participated in another interventional clinical study defined as having received the last intervention within 90 days or 5 half-lives of the study drug (whichever is longer) prior to dosing (Parts 1 and 2) vs. prior to first dosing (Part 3) of the study drug.
14. History or known hypersensitivity or allergy, or any form of allergic reactions to any excipients in the study drug or to humanized or murine monoclonal antibodies (or immunoglobulins).
15. Receipt of a vaccine within 4 weeks (COVID-19 vaccine within 6 weeks) prior to dosing and/or the intention to receive a vaccine during the study. Deviation from this should be judged by the Investigator and in dialogue with the Sponsor.
16. Recent confirmed COVID-19 infection, with less than 6 weeks between recovery and dosing of study drug.
17. Blood or plasma donation within 3 months of enrolment.
18. Positive urine drug screen or alcohol test at Screening or on Day -1.
19. History of drug or alcohol abuse, at the discretion of the Investigator, within past 12 months prior to Screening.
20. The subject currently smokes or uses nicotine-containing products. Former smokers will be eligible, provided they have not smoked for at least 1 month prior to Screening. Positive

cotinine test results at Screening or on Day -1 are reason for exclusion. Such positive test results can be repeated once to exclude environmental influence on the subject.

21. A positive pregnancy test or lactation at Screening or on Day -1.

The following exclusion criteria are only applicable for RA patients:

22. Intra-articular or systemic corticosteroid injection within 4 weeks prior to dosing.
23. Current or expected need of other immunosuppressant medication except MTX and/or intra-articular corticosteroid injections.
24. Known Gilbert's syndrome or Screening laboratory values indicating Gilbert's syndrome.

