8.4.3 Diet, Activities, and Other Restrictions

8.4.3.1 Concomitant Medication

From 2 weeks (or 28 days if the drug is a potential hepatic enzyme inducer) or 5 half-lives (whichever is longer) prior to Screening (or 4 weeks for RA cohort) until the EOS, prescribed or over-the-counter medication (including herbal remedies) is only allowed as described in exclusion criterion 6. Any new concomitant medication for treatment of AEs should preferably be discussed beforehand with the Investigator. The occasional use of paracetamol is allowed. Female subjects/patients are allowed to use oral contraception, a hormonal implant or hormonal intra-uterine devices as contraception. RA patients only (Part 2): If there is a medical need, local intra-articular corticosteroid injections are permitted at the discretion of a Principal Investigator.

If concomitant medication is needed during the study, this medication must be recorded on the eCRF, stating its generic name, time of administration, dose, route, frequency and duration, as well as the reason for administration.

The patients in the RA cohort will be treated with MTX. There should be at least 24 hours between administration of SOL-116 and the preceding MTX dose and at least 24 hours between administration of SOL-116 and the subsequent MTX dose. The patients in the RA cohort are allowed to use folic acid.

Part 3 only: Medications for incidental use (e.g., hay fever) may, at the Investigator's discretion, be allowed during the study.

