7.6 Exploratory Analyses

7.6.1 Exploratory Parameters

The exploratory parameters to be presented are:

- BSSL concentration
- Inflammatory biomarkers (except BSSL): CRP, ESR for all subjects/patients, and S-calprotectin and hsCRP (only RA patients)

The exploratory parameters will be summarized by using descriptive statistics of absolute values for each time point. Where applicable, change from baseline will also be calculated and summarized.

Exploratory data-driven analyses can be performed with the caveat that any statistical inference will not have any confirmatory value.

The PD (Exploratory) set will be used for analyses. Also, the Per-protocol (PP) set and the “all-treated set” will be used (see CSP section 10.2).

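### The PD (exploratory) set removes RA patients by their number of joint injections, and no planned summary separates biomarker values before and after an injection

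*SAP*

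**What the plan says.** SAP 6.1.5 and protocol 10.2 define the PD (exploratory) set in the same words. It contains treated participants without a protocol violation that could significantly affect the exploratory endpoints. The one example given is a count: "RA patients who received more than 2 intra-articular injections in large joints and/or 6 intra-articular injections in small joints during the study are excluded". The rule contains no date, visit or window.

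Protocol 8.4.3.1 allows these injections in Part 2: "If there is a medical need, local intra-articular corticosteroid injections are permitted at the discretion of a Principal Investigator". It sets no timing relative to biomarker samples. It does require that any concomitant medication be documented: "this medication must be recorded on the eCRF, stating its generic name, time of administration, dose, route, frequency and duration".

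The only time-based rule for steroid injections is exclusion criterion 22 in protocol 8.4.2, which concerns eligibility: "Intra-articular or systemic corticosteroid injection within 4 weeks prior to dosing".

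For the exploratory parameters, SAP 7.6.1 says "The PD (Exploratory) set will be used for analyses" and then adds the Per-protocol and All-treated sets. Protocol 10.8 agrees. SAP 7.2 analyses whatever data are available at each time point.

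**The concern.** The set exists to protect the exploratory biomarker results from events that would distort them. For an injection, what matters to a given value is whether the injection came before the sample. A count over the whole study does not capture that, and it can fail in two directions:

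- A patient at or below the limit keeps every value, including one taken shortly after an injection.
- A patient above the limit loses every value from the PD-set tables, including those taken before the first injection.

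The rule also does not follow from its own criterion. The set removes protocol violators, but an injection given for medical need under protocol 8.4.3.1 is not a violation.

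At stake is the reading of BSSL, CRP, hsCRP, ESR and S-calprotectin in a very small cohort: "In a cohort of up to 8 RA patients (6 active, 2 placebo". If steroids affect these markers, part of a change after dosing could be due to an injection, or an injection in a placebo patient could hide a difference. No planned table would show this.

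**Working it through.** The plan states no figure to reproduce, since no formal sample size calculation was made. The check applies the rule as written to the Part 2 schedule.

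**Inputs**
- hsCRP and S-calprotectin samples (protocol Table 5-2, footnote 16): "S-calprotectin and hsCRP determined prior to dosing and 4 hours post-dose on Day 1, on Day 2, on Day 4, on Day 21", then Days 49 and 90. That is 7 samples: pre-dose, 4 h, Days 2, 4, 21, 49 and 90. Table 8-4 also lists S-calprotectin 7 times.
- BSSL samples (Tables 5-2 and 8-4): 12, counting the optional Day 3.
- Cohort: 6 active, 2 placebo (SAP 5.3). SAP 7.1 pools placebo within each part, so Part 2 has 2 placebo patients.
- Planned statistics for these markers (SAP 7.1): n, mean, median, SD, minimum and maximum.
- Injection days and size of effect: not in the documents, so assumed below.

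**Step 1: how many injections leave a patient in the set.** The text does not settle whether the small-joint limit is more than 6 or is 6 or more.
- If more than 6: 2 large + 6 small = 8 injections, patient retained.
- If 6 or more: 2 large + 5 small = 7 injections, patient retained.

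**Step 2: post-injection values that stay in.** Take two large-joint injections on Day 5. The patient is under the count. The Day 21, 49 and 90 values, 3 of 7, are summarised without a flag.

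**Step 3: pre-injection values that leave the PD-set tables.** Take three large-joint injections, all from Day 60. The patient is over the count and is removed. Of the 7 hsCRP or S-calprotectin samples, 6 precede any injection. Of the 12 BSSL samples, 10 do. Removing one patient takes out 1/6 = 16.7% of the active arm or 1/2 = 50% of the placebo arm.

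**Step 4: do the other sets separate the values?** All-treated has no injection rule. Per-protocol removes only major violations or deviations, which a permitted injection is not. Neither uses injection dates.

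**Step 5: illustrative size.** Assume one injection lowers a marker by a fraction f at the next sample and patients' values are otherwise equal. With k of n patients affected, the arithmetic mean falls by f × k/n.

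| Assumed f | 1 of 6 active | 1 of 2 placebo |
|---|---|---|
| 30% | 0.30/6 = 5% | 0.30/2 = 15% |
| 50% | 0.50/6 = 8% | 0.50/2 = 25% |
| 70% | 0.70/6 = 12% | 0.70/2 = 35% |

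Under the same assumption, the median of 6 equal values would not move when one falls. With 2 patients the median equals the mean and shifts equally. With unequal values the shifts could be larger or smaller.

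**The case against.** The strongest case against this point has five parts.

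1. **Nothing is lost from the report.** A reader might infer that values of excluded patients are discarded. They are not. The All-treated summaries include them and individual listings cover all data. Concomitant medications are listed too, so with at most 8 patients a reader could match dates by hand. This stands, and it limits the point to the absence of a planned summary that uses timing.
2. **The scenarios may not occur.** Step 3 needs several injections late in a 90-day follow-up. Exclusion criterion 23 also mentions current or expected need for intra-articular corticosteroid injections. On one reading it screens out patients likely to need them, though the wording can also be read as an exemption. The documents give no expected frequency. This stands; the effect may be nil.
3. **Exclusion 22 is not a contradiction.** It is tempting to say that the plan bars one injection before dosing yet ignores several afterwards. But an eligibility washout and a post-dose analysis rule serve different purposes, and nothing in the documents makes 4 weeks the duration of a biomarker effect. This stands.
4. **Selection on outcome is inferred.** A reader might call the count a marker of uncontrolled disease. The documents say only medical need. That makes selection possible but does not show it, and setting aside post-injection values carries the same risk.
5. **The rule does not say corticosteroid.** SAP 6.1.5 speaks of intra-articular injections; the steroid reading comes from protocol 8.4.3.1. It is the natural reading, but it is a reading.

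None of this supplies a link between injection date and sample date, or explains why a permitted treatment is handled as a violation.

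**Conclusion.** The point holds as a flaw in a stated rule, at low severity. As written, the PD set can keep values taken just after an injection and can drop a patient's values from before any injection. No planned exploratory summary tells the two apart. The small-joint limit is also ambiguous.

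The size of any bias cannot be computed, because the documents give neither the frequency of injections nor the size or duration of their effect on these markers. The figures of 5% to 12% (one of 6 active) and 15% to 35% (one of 2 placebo) rest on the assumed 30% to 70% reductions and on equal underlying values. They show sensitivity in a small cohort and are not estimates.

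A reader might go further and infer that the Part 2 biomarker findings are biased or the trial's conclusions compromised. The documents do not support that. The endpoints are exploratory and descriptive, SAP 7.1 plans no statistical inference, and no primary or secondary result depends on this set.

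**What to change.** In SAP 6.1.5 and 7.6.1 and protocol 10.2:

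- Keep the general criterion for violations that affect the exploratory endpoints.
- Replace the injection-count exclusion with a flag on each biomarker value, derived from the recorded date of any intra-articular or systemic corticosteroid injection. This also removes the ambiguity over the small-joint limit.
- Keep all pre-injection values in the PD-set summaries, and present those summaries with and without post-injection values.
- If a finite window is preferred, such as the 4 weeks in exclusion 22, state it as a pre-specified assumption about duration of effect.
- Leave the All-treated summaries unchanged as the unfiltered view.

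With a first injection on Day 5, the filtered summary would keep 4 of 7 hsCRP or S-calprotectin values. With one on Day 60 it would keep 6 of 7.

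The cost is new wording, one derived flag and one further version of the tables. The date needed is already required on the eCRF. The filtered summary will have fewer late values, possibly n = 1 for placebo at a visit. Setting aside values after an injection given for medical need is itself conditional on post-dose disease activity, which is why both versions should be shown. SAP 3.1 locks and unblinds each part separately, so the change should be made before the Part 2 lock. It changes nothing in clinical management.
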